### **7.2.6. Leicester Cough Questionnaire (LCQ)**

The LCQ will be completed at Baseline, all subsequent visits and the Follow-up visit. This is a paper-based questionnaire that will be completed by the patient at the relevant visits. The results of the LCQ will be entered into the appropriate eCRF. Appendix 17.3 presents the LCQ.

## **7.3. Additional Endpoint(s) Assessments**

### **7.3.1. Weekly home spirometry measurements**

Patients will obtain spirometry readings at home on the same day and at approximately the same time each week (+/- 2 hours). Home spirometers will be dispensed at the Baseline visit; patients will be trained on the use of home spirometers prior to their departure from the Baseline visit.

### **7.3.2. Extent of fibrosis and lung volumes as assessed by HRCT**

HRCT scans will be obtained to measure the extent of fibrosis and lung volumes at Baseline and the Week 24 visits. These scans will be read and interpreted by a central reader.

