### Number of Patients

Approximately 100 patients will be treated; 50 each with 50 mg once daily or 100 mg twice daily

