**Notes for Tables 5 and 6:**

1. Follow-up visit will occur 28 days after the End of Study visit in Part B of the study.
2. A complete physical exam will be performed at Screening and Baseline visits. A modified physical exam including the patient's lungs and cardiovascular body systems will be performed at all other visits. For Safety Visits, only chest and skin exam are required.
3. Height is collected at the Screening visit only.
4. Blood samples for laboratory tests include: Chemistry (including AST and ALT), Hematology and Biomarkers (Blood samples for biomarkers will not be collected at Screening.) For Safety Visits, only AST and ALT are required.
5. Females of childbearing potential are required to take a urinary pregnancy test at each visit except the Follow-up visit.
6. Patients that pass screening and are scheduled to be randomized will receive a LCM to be worn for 24 hours and returned to the site at the Baseline visit. LCM will be worn for 24 hours at Visits 5 and 8. A paper diary will also be dispensed to the patient to record activities during the 24-hour period.
7. HRCT scans will be performed at Visits 2 and 8. The Baseline HRCT may be skipped if the HRCT for eligibility was performed less than 1 month prior to the Baseline visit.
8. Study material dispensation will occur at Visit 8 for those patients participating in Part B of the study.
9. Patients will be assessed for eligibility to participate in AP01-005 at EOS/Visit 12. Those enrolling in AP01-005 will use EOS/Visit 12 as their AP01-005 Baseline visit.
10. Patients enrolling in AP01-005 will not participate in the Follow-up visit.
11. Patients awaiting site approval of AP01-005 only.

Avalyn Pharma, Inc.  
AP01-002

Protocol V2.1  

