12 OCT2020

## **9 RANDOMIZATION AND BLINDING PROCEDURES**

### **9.1 Randomization**

Patients will be randomized in a 1:1 ratio to receive AP01 either 50 mg once daily or 100 mg twice daily; both regimens being administered by the eFlow. The randomization schema will be stratified by region (Asia-Pacific and Europe) and by disease severity (FVC < 50% predicted and FVC ≥ 50% predicted). The first 20 patients randomized in the study must have FVC ≥ 50% predicted at Screening. After the first 20 patients have been randomized, patients with FVC 40% < 50% predicted will be allowed to be randomized in the study but randomization for these patients will be capped at 20.

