### **9.2 Blinding**

This is an open-label study; no blinding restrictions are required.

Avalyn Pharma, Inc.  
AP01-002

Protocol V2.1  

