### 11.2.1 Significance Levels

No formal hypothesis tests are planned.

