4.2. Secondary Efficacy Endpoints

- Change from baseline in cough frequency as measured by LCM
- Change from baseline in the total KBILD score and in KBILD breathlessness and activity domains
- Change from baseline in the total LCQ score.
- Change from baseline in cough severity as measured by VAS
- Change from baseline in extent of fibrosis and lung volumes as assessed by HRCT
- Change from baseline in D_{LCO} .

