The following plot will be produced for extent of fibrosis and lung volumes as assessment by HCRT:

This document is confidential.

SAP Version: 3.0 (15JUL2021)
Controlled Document ID: **3903A.01**, Effective Date 29-Oct-2018
Filing requirements: TMF

Page 35 of 52

Statistical Analysis PlanSponsor: Avalyn Pharma, Inc.; Protocol No.: AP01-002

- Mean Extent of Fibrosis (or Lung Volume) Change from Baseline (\pm SD) vs. Weeks from Baseline (calculated based on visit date) for each lung region with lines for each treatment group.

A linear model will be used and differences between treatment groups between the change from baseline in whole lung extent of fibrosis and whole lung volume from Baseline to post-Baseline will be examined. Change from baseline will be the dependent variable and baseline whole lung extent of fibrosis (or whole lung volume), region, age at screening, sex, baseline D_{LCO} % predicted and baseline progression-related biomarker (CXCL13, CCL18, MMP3) values each categorized as $>$ Median level vs. \leq Median level, and time of HRCT (relative to baseline) will be included as covariates in the model.

All HRCT scan data will be presented in a listing including early termination and unscheduled visits.

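### The plan does not mask the central HRCT reader to regimen, although HRCT change is a secondary endpoint compared between arms

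*Protocol*

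**What the plan says.** Protocol 7.3.2 has HRCT obtained at Baseline and Week 24 to measure extent of fibrosis and lung volumes, and then says: "These scans will be read and interpreted by a central reader". SAP 8.2.5 repeats that sentence and adds no reading rules.

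On blinding, Protocol 9.2 consists of one sentence: "This is an open-label study; no blinding restrictions are required". SAP 3.6 repeats it. Neither makes an exception for anyone who assesses outcomes.

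The schedule notes say "HRCT scans will be performed at Visits 2 and 8", so each patient contributes one pair of scans. SAP 4.2 lists the measure among the secondary efficacy endpoints: "Change from baseline in extent of fibrosis and lung volumes as assessed by HRCT". SAP 8.2.5 compares the arms: "A linear model will be used and differences between treatment groups between the change from baseline in whole lung extent of fibrosis" and in whole lung volume. It also summarises change within each arm, and SAP 9.3 correlates the HRCT measures with FVC.

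Neither document mentions masking of the reader to regimen, patient identity, visit date or scan order. Neither mentions an imaging charter or a second reader, or says whether the measures are visual scores or software output.

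**The concern.** Patients and investigators know the regimen, and that knowledge can reach the questionnaires and effort-dependent spirometry. A centrally read scan is one of the few efficacy measures here that can be kept clear of it. Open-label dosing does not prevent masked reading.

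The direction that a reader might expect is on record. Protocol 4.1 reports that the DSMB saw a favourable FVC trend on 100 mg twice daily, and Protocol 1.2.4 describes that regimen as the optimal one. A reader who makes visual judgements and knows the regimen could lean the same way, even unintentionally.

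At stake is the between-arm HRCT contrast. Protocol section 2 has a separate objective for HRCT and another for comparing the regimens to guide later studies. A reader effect in that contrast would look like a dose effect, and no analysis in the SAP could separate the two.

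**Working it through.** **Step 1: what the documents establish.**

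| Question | Protocol | SAP |
|---|---|---|
| Who reads the scans? | A central reader (7.3.2) | The same (8.2.5) |
| Is the reader masked to regimen? | Not stated | Not stated |
| Is the reader masked to visit date or order? | Not stated | Not stated |
| General blinding rule | None required (9.2) | The same (3.6) |
| Are the arms compared on HRCT? | Efficacy analysis (11.5.1) | Linear model on change (8.2.5) |

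Taken together, nothing in the plan keeps the regimen from the reader, and nothing says that the reader is given it.

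**Step 2: no stated HRCT figure to reproduce.** Neither document gives an SD, effect size or power for HRCT. The SD of 4.5 in Protocol 11.1 is for change in FVC % predicted and does not carry over. What follows is illustration.

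**Step 3: regimen knowledge and the between-arm difference.** Inputs:
- n = 50 per arm, from the protocol synopsis ("Approximately 100 patients will be treated; 50 each with 50 mg once daily or 100 mg twice daily").
- Assumed SD of HRCT change: 4 to 6 points. Neither the values nor the unit is in the documents.
- Assumed reader shift between arms, b: 0.25, 0.5 or 1 point.

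Standard error of the arm difference: SE = SD × √(2/50) = SD × 0.2.
- SD 4: SE = 0.8
- SD 6: SE = 1.2

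If the true difference is zero, the chance that a two-sided 95% interval excludes zero is P(|Z + b/SE| > 1.96).

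| Shift b | b/SE, SD 4 | Chance | b/SE, SD 6 | Chance |
|---|---|---|---|---|
| 0 | 0 | 5.0% | 0 | 5.0% |
| 0.25 | 0.31 | 6.1% | 0.21 | 5.5% |
| 0.5 | 0.625 | 9.6% | 0.42 | 7.0% |
| 1 | 1.25 | 24% | 0.83 | 13% |

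The same calculation in SD units needs no assumed SD. A shift of 0.1 SD gives b/SE = 0.1/0.2 = 0.5 and a chance of 7.9%; 0.2 SD gives 1.0 and 17.0%.

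Fewer evaluable pairs widen the interval and lower these chances. With 40 per arm, SE = SD × √(2/40) = 0.89 to 1.34, and a 1-point shift gives about 12-20%. The bias in the point estimate stays at b whatever n is.

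**Step 4: scan-order knowledge.** If knowing which scan came first moves every patient's change by the same amount, that amount cancels from the arm difference. It does not cancel within an arm, where the standard error is SD/√50. A common shift of 0.1 or 0.2 SD equals 0.71 or 1.41 standard errors and cuts coverage of the within-arm 95% interval from 95% to 89.1% or 70.7%. The chances in Step 3 therefore apply to regimen knowledge only.

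**The case against.** **The blinding sentence concerns dosing.** It sits in the chapter on randomisation and blinding and follows from the open-label design. A reader might infer that the plan deliberately unmasks the HRCT reader, or that the scans were in fact read with the regimen known. The documents support neither. They do not mention the reader in that context, and nothing says that regimen or scan order is sent. This objection stands in full: the plan permits unmasked reading and goes no further.

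**Reading rules may be held elsewhere.** Protocol 12.3 lists HRCT results among data from outside sources, and a vendor's own procedures may mask the reader. That is possible. But the protocol refers to the clinical study manual for spirometry (7.2.1) and the cough monitor (7.2.2), and cites no manual or charter for HRCT.

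**The measures may be software-derived.** Lung volumes and fibrosis extent by lung region could be quantitative output, which would leave much less room for a reader to shift them. The documents do not say. This part stands as a limit on the concern and as a reason to state the method.

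**The consequence is limited.** The primary objective is safety, HRCT is one of six secondary efficacy endpoints in SAP 4.2, and "No formal hypothesis tests are planned". The Part B regimen change was attributed to FVC, not HRCT. All of this is right, and no planned decision depends on a nominal HRCT difference. It does not remove the point, because an estimate and its interval are biased whether or not a test is declared.

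**The remedy is late.** SAP version 3.0 is dated 15 July 2021, after the DSMB's October 2020 review of preliminary data, so some or all scans may already have been read. That shifts the useful remedy towards reporting how the reads were done.

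**Conclusion.** The concern holds in limited form. Both documents assign HRCT to a central reader without masking and waive blinding with no exception for that reader, so the plan permits a between-arm secondary endpoint to be scored with the regimen known.

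The size is unknown. The range of about 6% to 24% rests on an assumed SD of 4 to 6 points, assumed shifts of 0.25 to 1 point and 50 evaluable pairs per arm. It would not apply to fully automated measures. It shows that a small shift matters little and a shift of 1 point would matter, and it does not estimate what happened.

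A cheap improvement to how one secondary endpoint is measured is warranted. The safety objective and the FVC analysis are not affected. Random within-patient scan order and mandatory re-reading of every scan are choices on which statisticians may differ, and the point does not depend on either.

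**What to change.** 1. In Protocol 7.3.2 and 9.2 and SAP 3.6 and 8.2.5, state that scans go to the existing central reader de-identified and without regimen, with visit dates withheld where the reading method allows. The SAP's HRCT model needs scan timing as a covariate, but those dates can stay in the database and need not reach the reader.
2. In the same sections, state whether extent of fibrosis and lung volumes are visual scores or software-derived.
3. If scans have already been read, report whether the reader was masked. Treat unmasked visual reads as a limitation of the HRCT results, or re-read them masked if feasible.

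The first two items take a few sentences and minor de-identification work. They add no reader, visit, scan or patient, and leave the sample size and the analysis model unchanged. Re-reading would add reader time, which is why it is conditional.

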## **7.4. Safety Assessments**

All patients who enter the study will be assessed for safety. Safety will be monitored by observation of and direct inquiry regarding AEs at each visit after the first dose of study drug.

### **7.4.1. Adverse Events**

All AEs will be collected from informed consent through the Follow-up visit. Details regarding AE definitions, collection, recording, and reporting are found in Section 10.1.

### **7.4.2. Physical Examination**

A complete PE will be performed at the Screening and Baseline visits. This will include physical examination of the following body areas and systems: examination of general appearance, skin, head, neck (including thyroid), eyes, ears, nose, throat, heart, lungs, abdomen, lymph nodes, extremities, and nervous system.

A modified PE of the lungs and CV body systems will be performed at each subsequent visit.

A complete or modified physical exam is optional at unscheduled visits, per the investigator's discretion.

Body height will be measured at Screening only. Weight will also be measured at the Screening and Week 24 and 48 visits.

Avalyn Pharma, Inc.  
AP01-002

Protocol V2.1  
12 OCT2020

### **7.4.3. Vital Signs**

Blood pressure and pulse will be assessed at each visit. Patients should be comfortably seated for 5 minutes prior to blood pressure readings. Study staff will take care to select the appropriate cuff size for each patient. Respiratory rate and temperature will be measured at each visit.

### **7.4.4. Concomitant Medications/Therapies**

All concomitant medications/therapies collected throughout the study must be recorded on the Concomitant Medications and Therapies eCRF. The prohibited and allowed concomitant medications/therapies for the study are discussed in Section 8.9.1.

### **7.4.5. Electrocardiography (ECG)**

A 12-lead ECG will be recorded at Screening by the investigator or other designated, qualified individual from the study research team. ECGs will be assessed for clinical relevance including rhythm and repolarization.

### **7.4.6. Laboratory Assessments for Hematology, Serum Chemistry, Biomarkers and Urinalysis**

At each visit, clinical laboratory tests will be conducted at the study's central laboratory with the exception of biomarkers, which may be sent to a specialty lab. Clinical laboratory tests will include:

- Hematology: complete blood count with differential, platelet count
- Serum Biochemistry: bilirubin, alkaline phosphatase, sodium, potassium, chloride, bicarbonate, urea, creatinine, total protein, albumin, glucose, ALT, AST
- Urinalysis: pH, specific gravity, presence/absence of protein, glucose, blood
- Biomarkers: CXCL13, CCL18, MMP3 (progression-related) will be tested at Baseline only. CA19-9 and CA-125 (predictive of alveolar epithelial damage) will be collected at all visits except for the Screening visit.)

### **7.4.7. Pregnancy Testing**

At all visits except the Follow-up visit, a urinary pregnancy test will be performed for all FOCBP.

#### Contraceptive Requirements

Patients must be willing to comply with the contraceptive requirements of the study.

To prevent pregnancy in a FOCBP, FOCBP patients must agree to use one of the following contraceptive methods during the study and for 30 days after the last dose of IP:

- Abstinence from heterosexual intercourse OR
- Use a highly-effective form of contraception (e.g. hormonal contraception, or an intrauterine device) AND use of a barrier method by the female or her sexual partner.

Periodic abstinence (e.g., calendar, ovulation, symptothermal, post-ovulation methods) and withdrawal are not acceptable methods of contraception.

Avalyn Pharma, Inc.  
AP01-002

Protocol V2.1  
12 OCT2020

## **7.5. Pharmacokinetic Assessments**

This study will have no pharmacokinetic parameters assessed.

Avalyn Pharma, Inc.  
AP01-002

Protocol V2.1  
12 OCT2020

## 8. INVESTIGATIONAL DRUG INFORMATION AND MANAGEMENT

### 8.1. Investigational Drug Dose Regimen

Two dose levels/regimen combinations will be tested in this study:

- Pirfenidone 50 mg in 4 mL aqueous solution delivered once daily
- Pirfenidone 100 mg in 8 mL aqueous solution delivered twice daily

### 8.2. Dose Rationale

In addition to demonstrating safety and tolerability of AP01 multiple dosing in IPF patients, a key goal of the Phase 1b study is to select an optimal dosing regimen for further development of AP01. The initial dosing regimen was selected by formulation considerations, time and frequency of administration and local lung pharmacokinetics. Results from this study will help to elucidate whether therapeutic effect is dependent on peak dose, frequency of administration after a peak dose, or AUC in the lung.

Aqueous solubility limits the stability of the AP01 pirfenidone formulation concentration to 12.5 mg/mL. Time and frequency of administration are also important considerations; improved compliance is expected with fewer dose administrations per day and shorter administration times.

The 801 mg oral pirfenidone plasma pharmacokinetics have been well described. From this, one can estimate drug levels in the ELF and lung tissue from plasma concentrations. Assuming 50% of the drug is tightly protein-bound with the rest freely capable of local diffusion and with a known plasma  $T_{1/2}$  (2.4 hours), we may estimate AUC in both the ELF and lung tissue. Following an 801 mg oral dose, a measured plasma  $C_{max}$  is 7.9  $\mu\text{g/mL}$ , with the estimated ELF and lung tissue  $C_{max}$  of 3.9  $\mu\text{g/mL}$ . The  $AUC_{0-\infty}$  is 59.3  $\mu\text{g}\cdot\text{hr/mL}$  in plasma and estimated as 29.7  $\mu\text{g}\cdot\text{hr/mL}$  in ELF and lung tissue.

One can also estimate inhaled pirfenidone ELF pharmacokinetics from a single collected BAL fluid sample from healthy volunteers. Due to the time to administer anesthesia and perform the procedure, BAL collection is typically 30 - 50 minutes post-drug administration, which is several  $T_{1/2}$  from the true  $C_{max}$  seen at the end of inhaled administration. Therefore, because the ELF clearance  $T_{1/2}$  is unknown, one can only estimate the ELF pirfenidone  $C_{max}$  and local lung AUC. To strengthen this estimation, a large animal sheep pharmacokinetic study was performed. Sheep were administered inhaled pirfenidone and both serial BAL and plasma samples collected. Analysis of this data provided a pirfenidone plasma/ELF pharmacokinetic relationship curve, which was used to extrapolate the single human ELF data point back to  $C_{max}$  and estimate AUC. In normal human volunteers, the 100 mg dose provided an average ELF  $C_{max}$  of 135.9  $\mu\text{g/mL}$  and an  $AUC_{0-last}$  of 54.5  $\mu\text{g}\cdot\text{hr/mL}$ . With these data, one can also then confirm adequate pirfenidone ELF delivery in the IPF population in the absence of BAL fluid sampling by correlating obtained plasma levels and 24-hour urine collections between normal volunteers and IPF patients.

The 24-hour urine collection in the normal human volunteers BAL cohort compared to the IPF cohort was similar on average but with less variability (40.2  $\pm$  20.5 mg vs. 42.2  $\pm$  14 mg). Since the IPF cohort has less lung surface area but the same absorption, this suggests that the IPF cohort had higher  $C_{max}$  ELF levels. The  $C_{max}$  plasma levels in the IPF cohort were lower than the volunteer cohorts, but absorption was prolonged, also suggesting the ELF AUCs were similar or superior to the BAL cohort.

Avalyn Pharma, Inc.  
AP01-002

Protocol V2.1  
12 OCT2020

There are other preclinical and clinical observations that provide considerations for potential dose regimens. The first is that the inhaled  $C_{\max}$  with the 100 mg dose exceeds the pirfenidone half maximal inhibitory concentration ( $\sim 25 \mu\text{g/mL}$ ) from in vitro models and nears the observed half maximal effective concentration ( $EC_{50}$ ) ( $\sim 100 \mu\text{g/mL}$ ) in animal models of bleomycin injury. As noted before, the  $C_{\max}$  in the ELF of the 801 mg oral dose is  $3.9 \mu\text{g/mL}$  and does not approach the required concentrations from in vitro and in vivo models of lung injury. These observations suggest that a higher  $C_{\max}$  may improve efficacy. Second, as noted above, preclinical models of IPF using bleomycin suggest that efficacy is correlated with  $C_{\max}$  rather than AUC, this finding would be ideal for an aerosol dose with high ELF concentrations and fast clearance. Although these same animal models suggest that once a day dosing can be effective, the duration of action after a peak dose in IPF patients is not known.

The high dose chosen for the Phase 1b study is 100 mg administered twice daily. The 100 mg dose based on the modeling noted above would provide an average  $C_{\max}$  in the ELF of  $135.9 \mu\text{g/mL}$  and an  $AUC_{0-18 \text{ hr}}$  of  $54.5 \mu\text{g}\cdot\text{hr/mL}$ . The  $C_{\max}$  is approximately 35-fold higher than what is achieved with the oral 801 mg dose, with the total  $AUC_{0-18 \text{ hr}}$  2-fold higher. IPF's pathogenesis is postulated to pivotally depend upon alveolar epithelial cell damage. This dose would provide dramatically higher ELF  $C_{\max}$  and a daily cumulative AUC with the twice daily aerosol dose 1.5-fold higher compared to a three times daily 801 mg oral dose. The 100 mg aerosol dose requires a 9 - 15 minutes administration time.

The second dose chosen for the Phase 1b study is 50 mg administered once daily. In the Phase 1 dose escalation study, the plasma pharmacokinetics were proportional to the dose. Assuming proportionality, the 50 mg once daily dose would have a  $C_{\max}$  17-fold higher than the oral 801 mg dose, and a total 24-hour AUC in the ELF that would be 2/3 of the 801 oral three times daily regimen. The administration time of the 50 mg dose is expected to be 5 - 7 minutes and a shorter regimen would likely lead to more compliance, better patient acceptance and perhaps fewer adverse respiratory effects.

Both of these doses will have substantially less systemic pirfenidone exposure compared to the 801 mg oral dose. Following an 801 mg oral dose, the peak plasma mean concentration is  $7.9 \mu\text{g/mL}$  and the  $AUC_{0-18\text{hr}}$  is  $60.9 \mu\text{g}\cdot\text{hr/mL}$ . Following a 100 mg inhalation, the peak plasma mean concentration is  $1.7 \mu\text{g/mL}$  and the  $AUC_{0-18\text{hr}}$  is  $4 \mu\text{g}\cdot\text{hr/mL}$ . Therefore, the 100 mg nebulizer dose leads to less than 1/15, and the 50 mg dose 1/30, the systemic exposure of the oral dose.

No clinical study has examined fewer than three oral pirfenidone doses per day. Since oral pirfenidone is taken at meals, the time between dinner and breakfast is usually twelve hours, suggesting the duration of action is at least that long. Like inhalation, the three times daily oral regimen delivers a short-duration peak with very low trough levels. Testing a 100 mg twice daily regimen would mimic the duration between evening and morning dose and would also increase the AUC in the ELF over a 24-hour period by 1.5-fold compared to the 801 mg three times daily oral dose. If efficacy is driven by  $C_{\max}$  rather than AUC, the 100 mg twice daily and 50 mg once daily doses would provide a 34-fold and 17-fold higher peak concentration, respectively, than is achieved from an 801 mg oral dose. The 50 mg once daily regimen would provide a 17-fold higher peak concentration than is achieved from an 801 mg oral dose. The 50 mg once daily regimen was chosen to test the hypothesis that only once daily dosing is adequate and efficacy is driven by  $C_{\max}$  in the ELF. The 100 mg twice daily regimen was chosen to test whether efficacy is also dependent on total ELF AUC or multiple daily peaks.

